## **OBJECTIVES:**

Primary Aim: To test, in a 3-month randomized controlled trial, the efficacy of the mHealth intervention on changing consumption of targeted healthy and less healthy foods/beverages in children with ASD who are picky eaters. We hypothesized that, by the end of the intervention, children in the intervention group, but not children in the education group, would show a significant increase (expressed as % change from baseline) in intake of FV and a decrease in calories consumed from salty and sugary snacks and SSB.

Secondary Aim: To perform a comprehensive evaluation of the mHealth intervention by measuring parent and child engagement, motivation, user friendliness, and ease of use.

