## **CHARACTERISTICS OF THE STUDY POPULATION:**

### **1. Target Population and Accrual:**

The study aimed to include 46 racially/ethnically diverse boys/girls with ASD, ages 6-10 years, and their parent/legal guardian (referred to 'parent' for ease of use). The age range was chosen to ensure that children have the cognitive skills to interact with the technology. Our multi-pronged recruitment plan utilized the CHOP health system and community-based organizations throughout Philadelphia. The study was open to subjects of all races and ethnicities. Parents must be the children's primary caregiver (i.e., person responsible for grocery shopping/feeding). Children and parents must have access to a smartphone or tablet to be eligible for study participation. For this exploratory trial, we aimed to recruit a well-defined, homogenous group of children to determine the efficacy of this intervention. Only children without significant developmental delay (i.e., IQ  $\geq 80$  and comparable verbal ability) were enrolled to increase the likelihood of comprehension and engagement with the technology. Children with a range in weight were included to explore if the intervention is equally effective in normal-weight and overweight/obese children.

This project's primary purpose was to evaluate feasibility, acceptability, and utilization of the mHealth intervention and to obtain preliminary effect size estimates. A power analysis was conducted (PASS software, Version 11, NCSS LLC, Kaysville, UT) for Primary Aim 2 using 3-month changes in intake of targeted healthy foods (FV) as the primary outcome variable. The estimated mean ( $\pm SD$ ) for baseline FV intake ( $2.57 \pm 1.20$  servings/day) was derived from our pilot study in children with ASD. Based on this estimate, a sample size of 46 children and an attrition rate of 10%, we had 80% power to detect a statistically significant increase in FV intake of 1.1 servings/day (or 43%) in the intervention group relative to the education group at the alpha 0.05 level, based on a two sample t-test. The magnitude of this increase is comparable to that achieved in behavioral interventions in TDC and represents ~one-fifth of the RDA of FV for children of that age.

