### **1. Study Instruments:**

**Assessment of Intake of Target Foods:** Targeted healthy foods included FV (fresh, canned, frozen). Parents were instructed to omit energy-dense toppings/sauces on FV. Targeted less healthy foods included 1) SSS (e.g., all types of chips, popcorn, pretzels, party mixes, ice cream, candy, cookies, cakes/pies, sweet rolls, pastries) and 2) SSB (e.g., sugar-sweetened sodas, fruit drinks/punches and fruit juices, sport drinks, and energy drinks). Dietary goals were set by parents and tailored to children's preferences and sensory sensitivities. Children's intake was assessed at baseline and at the end of the intervention using the telephone-based 24-hr dietary recall method; the gold standard for self-reported intake. Each assessment consisted of 3 unannounced recalls (2 weekdays, 1 weekend day), which was conducted by research dietitians from the CHOP Center for Human Phenomic Science. Dietitians were blinded to families' group assignment. During each recall, they asked parents, with help from the children, to describe all foods/beverages consumed by their children during the prior 24 hours and provide detailed information about portion sizes/preparation methods. Data were analyzed for daily FV intake (servings/day; cup equivalents) and calories consumed from SSB/SSS using the University of Minnesota Nutrition Coordinating Center's Food and Nutrient Database. All data were averaged across the 3 days.

**Child Height and Weight Measures:** At baseline and at the end of the intervention, children had their heights and weights measured. Measurements were taken in triplicate with a portable scale/stadiometer by a trained staff member in children's homes with children wearing light clothing (no shoes). Child age- and sex-specific BMI percentiles and z-scores were calculated using the CDC Growth Charts 2000. Children were classified as normal-weight (BMI-for-age 5–84th percentile), overweight (BMI-for-age 85–94th percentile), or obese (BMI-for-age ≥95th percentile).

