### **5. Statistical Analysis:**

To test Primary Aim 2, a mixed-effects linear model with repeated measures assessed 3-month changes in children's FV (cups/day) and SSB/SSS (calories/day) intake by group. The fixed factor effects in all models were group (incentive, control) and time (baseline, month 3). The group-by-time interaction was tested and removed if not significant. Analysis of covariance assessed if the intervention is equally successful in boys/girls, children of various ages/weights, and children with typical/atypical sensory sensitivity. For Secondary Aim 2, data from log files and questionnaires were analyzed and open-ended responses from the semi-structured interview were coded, compiled into categories, and grouped into themes using a general inductive approach.  $P$  values were two-sided and  $P<0.05$  was considered significant for all tests. First, analyses were conducted with all participants included. Then, a sensitivity analysis were conducted that included only participants who actively participated in the intervention.

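### FV intake is named and powered as the primary outcome, but the objectives and analysis set SSB/SSS calories beside it at the same 0.05 level with no ranking or success rule

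*Combined protocol and SAP*

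**What the plan says.** Three places bear on what counts as the primary test.

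- **Target Population and Accrual (section 1).** The power analysis was done "using 3-month changes in intake of targeted healthy foods (FV) as the primary outcome variable". Its result is also for FV alone: "we had 80% power to detect a statistically significant increase in FV intake of 1.1 servings/day (or 43%) in the intervention group". The comparison is between the two groups, by t-test at alpha 0.05. No effect size, SD or power is given for snack or beverage calories.
- **Objectives.** The primary hypothesis is joint. It predicts an increase "in intake of FV and a decrease in calories consumed from salty and sugary snacks and SSB".
- **Statistical Analysis (section 5).** One sentence, under the primary aim, applies the mixed model to FV and to SSB/SSS calories alike. That section closes by making every P value two-sided and by saying that a value below 0.05 "was considered significant for all tests".

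No section ranks the outcomes, adjusts alpha, or says whether one or all must succeed. The number of calorie outcomes is also open. Study Instruments numbers SSS and SSB as two food categories, but then describes the analysed quantity as "calories consumed from SSB/SSS", which reads more naturally as one total.

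The Statistical Analysis section calls the aim Primary Aim 2, while the Objectives list one unnumbered primary aim. The content matches, so I take them to be the same aim.

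**The concern.** The analysis section is where a reader looks for the decision rule, and there FV and SSB/SSS stand level. A result on SSB/SSS calories alone, at P below 0.05, could then be read as meeting the primary aim. That outcome has no power calculation, and the sample-size text does not call it primary.

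What the stated 5% and 80% describe depends on a rule the plan does not give. If either outcome can carry the aim, 5% is not the error rate of the primary claim. If both are needed, as the joint wording of the hypothesis suggests, 80% is not the power for that claim.

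**Working it through.** **Inputs from the sample-size text:** 46 children, 10% attrition, baseline FV mean 2.57 and SD 1.20 servings/day, difference 1.1 servings/day, alpha 0.05, two-sample t-test. Two-sided testing comes from the Statistical Analysis section. **Assumptions:** 1:1 allocation, which is not stated, and the baseline SD used as the SD of the change.

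**1. The plan's own figure.** Evaluable children: 46 × 0.90 = 41.4, or about 20 + 21. Standardised difference: 1.1 / 1.20 = 0.917. Power from the noncentral t distribution:

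| Evaluable per arm | Power |
|---|---|
| 20 and 20 | 80.6% |
| 20 and 21 | 81.6% |
| 21 and 21 | 82.6% |

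The detectable difference at 80% power is 1.09 with 20 per arm and 1.06 with 21, both rounding to 1.1. Also 1.1 / 2.57 = 42.8%, which rounds to the stated 43%. The 80% reproduces, for FV alone.

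**2. Reading A: FV is the sole primary outcome.** There is one test at 0.05, so the primary error rate is 5% and the power is as stated. Nothing is missed.

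**3. Reading B: a win on any one outcome supports the aim.** For k independent tests, familywise error = 1 − 0.95^k.

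- Two tests: 1 − 0.95² = 9.75%.
- Three tests (SSB and SSS separate): 1 − 0.95³ = 14.26%.

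For two-sided tests on jointly normal statistics, independence is the worst case, so these are ceilings. The correlation between outcomes is not given. Simulation at assumed values gives:

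| Assumed correlation | Two tests | Three tests |
|---|---|---|
| 0.3 | 9.5% | 13.6% |
| 0.5 | about 9.1% | 12.5% |
| 0.8 | 7.8% | 9.9% |

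Counting only results in the hypothesised direction, one test has a 2.5% error rate. Two independent tests have 1 − 0.975² = 4.9%, and three have 1 − 0.975³ = 7.3%.

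**4. Reading C: all outcomes must succeed.** No alpha adjustment is needed. Joint power cannot exceed the power for FV alone, and it cannot be computed without an SSB/SSS effect and SD. As illustration only, with two independent outcomes, joint power = 0.80 × p, where p is an assumed power for SSB/SSS:

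- p = 0.50: 0.80 × 0.50 = 40%
- p = 0.80: 0.80 × 0.80 = 64%
- p = 0.90: 0.80 × 0.90 = 72%

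At p = 0.80 and an assumed correlation of 0.5, joint power is 69%.

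**The case against.** The strongest reply is that the sample-size text is the only place that labels an outcome as primary, and it names FV. An aim can hold one primary outcome and supporting ones, and the plan never claims 80% power for a joint hypothesis. This stands: Reading A is available, and on it both stated figures are correct. It does not settle the matter, because the label appears only inside a power calculation and neither the hypothesis nor the analysis carries it through.

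A second reply is that the trial is called exploratory and that its main purpose is given as feasibility and preliminary effect sizes. Familywise control matters less there. This also stands and lowers the severity. It does not remove the point, since the Objectives speak of testing efficacy and the analysis declares a significance threshold.

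A third reply is that the three-test count has weak support: the numbered items in Study Instruments define foods, and the analysis writes SSB/SSS as one quantity. That is fair, so two tests is the better-supported count and 14.3% is conditional.

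A reader might go further and infer that the plan must have either a false-positive rate of 10–14% or a shortfall in power. The documents do not support that. It leaves out Reading A, treats independence ceilings as the actual rate, and needs an SSB/SSS power that is nowhere stated.

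**Conclusion.** The point holds as an inconsistency between sections. FV is named and powered as primary in one place, while the hypothesis and the analysis set SSB/SSS calories beside it without rank or rule.

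The consequence depends on the reading. With FV as sole primary there is no numerical error. With either outcome sufficient, familywise error is at most about 9.8% for two tests, about 9.1% at an assumed correlation of 0.5, and up to 14.3% only if SSB and SSS are tested separately. With both required, the 80% does not describe the hypothesis, and the true figure cannot be derived from the documents.

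No passage says that an SSB/SSS-only result would count as success; the plan simply does not rule it out. Given the exploratory purpose, severity is low to moderate. The point is worth acting on because the correction is cheap and settles what may be concluded.

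**What to change.** - In the Objectives and Statistical Analysis sections, state that the group-by-time effect on FV intake is the single primary test, matching the sample-size text, and that the 80% power applies to FV only.
- Define total kcal/day from SSB plus SSS combined as the secondary outcome. Test it at 0.05 only if FV is significant. Otherwise report it as an estimate with a 95% confidence interval.
- The document is written in the past tense. If this order is added after results are known, disclose it as post hoc.

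**Cost.** Wording only, with no extra participants. FV keeps its full 0.05 level and stated power. By comparison, a Bonferroni split with about 41 evaluable children would cut FV power to about 73% for two tests (alpha 0.025) or 67% for three (alpha 0.0167). The downside is that an SSB/SSS effect cannot be claimed as confirmed if FV fails.

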#### **STUDY DESIGN:**

A 3-month randomized controlled trial tested the efficacy of a mHealth intervention on changing consumption of targeted healthy (FV) and less healthy (SSB/SSS) foods/beverages in children with ASD who are picky eaters. In this exploratory trial, parent-child dyads were randomly assigned to either an mHealth (+ parent training) intervention group or an education group. Parents in the intervention group received the mHealth nutrition intervention plus training in behavior change strategies and an explanation of the dietary targets. Parents in the education group received a handout with general educational information about healthy eating and an explanation of the dietary targets. Parent trainings in both groups were matched for in-person contact time. Families in the education group received access to the mHealth intervention after they completed the study.

At the end of the intervention, parents in the intervention group were asked to complete a semi-structured interview and a brief questionnaire, which asked them to provide feedback on the usefulness and relevance of the mHealth technology, parent and child engagement and motivation, and to evaluate key features of the mHealth intervention such as user friendliness, ease of use, and technical or time barriers. Children in the intervention group were asked to complete a brief questionnaire that assessed level of enjoyment, learning, and understanding of the mHealth technology.

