**Questionnaires:** During the telephone screening, parents were asked to complete the Picky Eating subscale of the Child Feeding Questionnaire (CFQ), which consists of the following items: 1) "My child's diet consists of only a few foods"; 2) "My child is unwilling to eat many of these foods that our family eats at mealtimes"; 3) "My child is fussy / picky about what she eats." A child was defined as a picky eater if the parent endorsed at least 2 out of the 3 items. Parents were asked follow-up questions to determine whether a child's pickiness was related to the intervention's targeted healthy and less healthy foods. During the baseline visit, parents completed a Demographic Questionnaire and the 38-item Sensory Profile, 2nd Edition (short form), which assessed children's sensory processing abilities, including oral sensory sensitivity (e.g., sensitivities to food tastes/textures). Children were categorized as having typical or atypical oral sensory sensitivity based on classifications specified by Dunn.

**Evaluation of mHealth Intervention:** We evaluated the mHealth intervention using the following strategies: 1) Engagement: The mHealth platform kept an automatic log of all user activities, including subjects' log-in frequency, duration of use, features used, goal/progress tracking, number of points and rewards awarded, etc. These log files were automatically generated by the software and enabled us to monitor participants' compliance with the intervention; 2) Semi-structured interviews and brief questionnaires: At the end of the intervention, parents in the intervention group were asked to complete a semi-structured interview and a brief questionnaire, which asked them to provide feedback on the usefulness and relevance of the mHealth technology, parent and child engagement and motivation, and to evaluate key features of the mHealth intervention such as user friendliness, ease of use, and technical or time barriers. Children in the intervention group were asked to complete a brief questionnaire that assessed level of enjoyment, learning, and understanding of the mHealth technology

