#### **4. Administration of Surveys and/or Process:**

Telephone Screening: The telephone screening involved review of information to determine initial eligibility criteria. In addition, during the screening phone call verbal consent was obtained for completion of the baseline dietary recall interviews with the parent prior to the baseline visit.

Baseline Study Visit: The baseline study visits included the full written consenting/assenting process, measurement of child height and weight, completion of questionnaires, and, for families in the intervention group, orientation to the technology and installation of the software on participants' smartphones. This visit lasted approximately 90 minutes.

3-Month Study Visit: The 3-month study visit (end of intervention) included measurement of child height and weight and, for families in the intervention group, a semi-structured interview and two brief questionnaires to evaluate the mHealth intervention. This visit lasted approximately 60 minutes.

Dietary Recalls: Children's intake was assessed at baseline and at the end of the intervention using the telephone-based 24-hr dietary recall method. Each assessment consisted of 3 unannounced recalls (2 weekdays, 1 weekend day), which were conducted by research dietitians from the CHOP Center for Human Phenomic Science. Each recall lasted approximately 20 minutes.

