### **STUDY PROCEDURES:**

#### Randomized Controlled Trial:

Intervention Group: At baseline, parents in the intervention group received a comprehensive parent training which 1) provided skills training in the five core behavior change strategies and 2) explained the nutritional goals and targeted foods/beverages for the study. The training modules were designed by a behavioral strategist and clinical psychologist, a clinical psychologist, and a nutrition scientist. The modules reviewed examples of the targeted foods/beverages and provided training in how to present feeding opportunities, incorporate healthy target foods in daily family meals and snacks, and substitute the less healthy target foods/beverages for healthier options. The training also addressed how parents can overcome resistance in children trying new foods using differential attention and positive reinforcement techniques. It included instructions on how to use the mHealth technology and showed parents how to set dietary goals, select real-life prizes, award points, and determine the allotted timeframe and number of points it will take for the child to earn a prize. The mHealth intervention was personalized for each child to take into account individual differences in children's food preferences, level of picky eating, sensory sensitivities, etc. Specifically, the mHealth technology enabled parents to tailor the selection of food choices available to the child and customize, with input from the child, food preparation methods (e.g., raw or cooked, seasonings to be added). The training also included a training module for the children to show them how to navigate the technology, orient them to the nutrition intervention, and explained the reward system. Research staff assisted with the software installation on the families' electronic devices and parents were encouraged to use the technology as frequently as possible during meal and snacks times over the course of the 3-month intervention.

**Education Group:** Parents in the education group were instructed to review a handout, which provided general educational information about healthy eating. It explained the nutritional goals and targeted foods/beverages for the study, but it did not provide parent skills training in the core behavioral strategies. This condition mimiced what families may receive during a routine well-child visit.

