Parents in both groups were encouraged to promote children's intake of the healthy target foods and limit their intake of the less healthy target foods/beverages on a daily basis for the next 3 months.

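### Does the undefined active-participant sensitivity analysis, covered by the general 5% rule, need a change to the plan?

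*Combined protocol and SAP*

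**What the plan says.** The Statistical Analysis section sets out a mixed-effects model for three-month change by group. It runs this on all participants first, and then "a sensitivity analysis were conducted that included only participants who actively participated in the intervention". The same section states that a two-sided P below 0.05 "was considered significant for all tests", with no exemption.

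Engagement data are described under Study Instruments. The platform automatically logged "log-in frequency, duration of use, features used, goal/progress tracking, number of points and rewards awarded", and the section says that these logs allowed compliance to be monitored. It sets no threshold. The Study Procedures section sets no minimum either: "parents were encouraged to use the technology as frequently as possible during meal and snacks times".

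On the comparison arm, the Study Design section says: "Families in the education group received access to the mHealth intervention after they completed the study". Outcome data were collected in both arms. For the diet measure, "Each assessment consisted of 3 unannounced recalls (2 weekdays, 1 weekend day"); for the final visit, "The 3-month study visit (end of intervention) included measurement of child height and weight". Both arms also had the same dietary task: "Parents in both groups were encouraged to promote" the healthy target foods and limit the others.

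**The concern.** Three gaps come together. First, no criterion for active participation is given, and none can be inferred, because families were asked only for as much use as possible and at least five log measures could serve. Second, the criterion cannot be applied to education families, who have no in-trial log. Read literally, none of them qualifies; if all are kept, a self-selected subset of one arm is compared with the whole of the other. That comparison is no longer randomised and can be biased in either direction. Third, the general significance sentence reaches this analysis.

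The worry is that the intervention could be declared effective in active users when the all-participants result is null, on a criterion that the plan never fixed. Calling the analysis a sensitivity analysis could also lead readers to take it as a check of robustness, which filtering one arm on behaviour after randomisation does not provide.

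**Working it through.** **Inputs.** From Target Population and Accrual: 46 children, 10% attrition, baseline FV intake 2.57 (SD 1.20) servings/day, detectable difference 1.1 servings/day, 80% power, two-sample t-test at 0.05. Assumed, because the documents do not give them: 1:1 allocation, the share of intervention children counted as active (10 or 16 of 21), and the correlation r between engagement and a child's own FV change.

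**Step 1: the plan's own figure.** 46 × 0.9 = 41.4, so about 21 versus 20. Noncentrality = 1.1 / (1.20 × √(1/21 + 1/20)) = 1.1 / 0.375 = 2.93 on 39 degrees of freedom. Two-sided power is 81.6% (80.6% with 20 versus 20). The stated 80% reproduces, and it belongs to the all-participants analysis, which this concern does not touch.

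**Step 2: the event at stake.** This is an all-participants test that is not significant together with a restricted test that significantly favours the intervention. Simulation used 100,000 trials per scenario, no true effect, and all 20 education children kept. The test was a t-test on change, which with two complete time points is the group-by-time test of the planned model. With one fixed criterion and r = 0:

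| Kept | At least one test significant | Less 5% for the full test | Half, favouring the intervention | Event simulated directly |
|---|---|---|---|---|
| 16 of 21 | 6.9% | 1.9% | 0.95% | 0.9% |
| 10 of 21 | 7.8% | 2.8% | 1.4% | 1.4% to 1.5% |

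The at-least-one rates contain the ordinary 5% of the main test and results against the intervention, so they overstate this harm.

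**Step 3: if engagement is related to outcome.** With r = +0.3 the event occurs in 3.2% (16 kept) or 6.9% (10 kept) of trials; with r = +0.5, in 6.3% or 15.4%. With 16 kept and r between −0.3 and +0.3, the restricted test alone rejects in 4.9% to 6.7% of trials, so a mild filter does little.

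**Step 4: size of the bias.** At an SD of change of 1.20 the bias is:

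| Kept | r = ±0.3 | r = ±0.5 |
|---|---|---|
| 16 of 21 | ±0.14 | ±0.23 |
| 10 of 21 | ±0.29 | ±0.48 |

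The 1.20 is a baseline SD. The SD of change is 1.20 × √(2(1 − c)), where c is the correlation between baseline and month 3 (equal variances assumed). For c = 0.3 this is 1.42, for c = 0.5 it is 1.20, and for c = 0.7 it is 0.93. The bias scales in proportion: the largest value, 0.48 / 1.20 = 0.40 SD, becomes 0.40 × 0.93 = 0.37 to 0.40 × 1.42 = 0.57 servings/day. The sign and size of r cannot be obtained from the documents.

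**Step 5: what a change would do.** Removing the restricted analysis from the significance rule while reporting its 95% confidence interval leaves the estimate, the interval and the selection as they are. An interval that excludes zero tells the reader the same as P < 0.05. Filtering both arms on completed recalls and visits would pick out completers, not active users. Among the 41 children with outcomes assumed here, it would remove nobody.

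**The case for a change.** The best case for acting is that the gaps are textual and do not depend on any assumed correlation. A sensitivity analysis is normally read as testing robustness, and selecting one arm on later behaviour changes the comparison instead. The exploratory label does not lift the 5% rule, and the Objectives do state an efficacy aim. An open criterion also invites choice. If ten criteria (five log measures, two cut-offs each) were all tried, none related to outcome, the event in Step 2 would occur in 4.5% to 6.1% of trials. A remedy would cost only a few sentences.

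Part of this stands. Once only the intervention arm is filtered, the result is non-randomised, and neither agreement nor disagreement with the main result shows robustness. The ten-criteria case carries little weight: the cut-offs and the correlations between measures are assumed, and nothing in the documents suggests that criteria were tried in turn. That the restricted result would be declared significant in its own right is an inference from a generic sentence about alpha; no section plans such a claim. The data source is named, and the wording reads naturally as a filter on intervention families alone, which an analyst would apply without difficulty.

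**Conclusion.** No change to the plan is needed. The missing cut-off and the missing education-arm rule are real, but they concern a secondary look that follows the all-participants analysis, in a trial whose accrual section gives feasibility and preliminary effect sizes as its main purpose. No conclusion is tied to it, and sample size, power and error rate of the main analysis are unaffected.

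The added risk of the misleading event is about 0.9% to 1.5% per outcome under one fixed criterion unrelated to outcome. It rises to between 3.2% and 15.4% only under assumed positive correlations of 0.3 to 0.5. These figures rest on 21 versus 20 children, 10 or 16 kept, and an unfiltered education arm.

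What remains is ordinary reporting, and the section's past tense suggests that the work is done. A report would be expected to give the log measure and cut-off, when they were chosen relative to seeing outcomes, how many children met them, and how education families were handled. It would be expected to show the result as exploratory and non-randomised beside the all-participants estimate. If a report instead rested an efficacy claim on the active users alone, that would be a fault of the report, to be judged there.
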